## 6.8 Biomarker Study

Quizartinib-related biomarkers and biomarkers that allow the prediction of efficacy and others of quizartinib will be explored. Details including the handling of specimens for each study item will be specified in separate procedures. The date and time of specimen collection will be recorded in the CRF.

### 6.8.1 FLT3-ITD Status and c-KIT Mutations

The following specimens will be collected before the start of administration of coadministered drugs (cytarabine and the anthracycline drug): 1 mL of bone marrow liquid or 2 mL of peripheral blood for analysis of the FLT3-ITD status, and 1 mL of bone marrow liquid or 7 mL of peripheral blood for analysis of c-KIT mutations. The specimens under refrigeration will be submitted to the agency contracted by the sponsor to collect the specimens.

### 6.8.2 Phosphorylated FLT3, STAT5, and c-KIT Protein Levels in Blood

After 2 mL of blood is collected from each patient as specified in "Table 6.8-1 Blood Collection Points (Phosphorylated Protein Levels in Blood)," the plasma specimens will immediately be stored in a frozen state at  $-90^{\circ}\text{C}$  to  $-70^{\circ}\text{C}$ . The specimens in a frozen state will be submitted to the agency contracted by the sponsor to collect the specimens.

Table 6.8-1 Blood Collection Points (Phosphorylated Protein Levels in Blood)

Treatment Cycle	Treatment Day	Blood Collection Point (Acceptable Limit)
Remission induction therapy	Day 8	Pre-dose
Cycle 1	* First day of quizartinib administration	2 hours ( $\pm 10$ minutes) post-dose
		4 hours ( $\pm 10$ minutes) post-dose
		6 hours ( $\pm 10$ minutes) post-dose
	Day 9	Pre-dose
	Day 15	Pre-dose
	Day 21	Pre-dose
	* Last day of quizartinib administration	

### 6.8.3 Inhibitory Activity of Plasma Quizartinib on Phosphorylated FLT3 Protein

After 5 mL of blood is collected from each patient as specified in “Table 6.8-2 Blood Collection Points (Inhibitory Activity of Plasma Quizartinib on Phosphorylated FLT3 Protein),” the specimens will be prepared and immediately be stored in a frozen state at  $-90^{\circ}\text{C}$  to  $-70^{\circ}\text{C}$ . The specimens in a frozen state will be submitted to the agency contracted by the sponsor to collect the specimens.

Table 6.8-2 Blood Collection Points (Inhibitory Activity of Plasma Quizartinib on Phosphorylated FLT3 Protein)

Treatment Cycle	Treatment Day	Blood Collection Point (Acceptable Limit)
Remission induction therapy	Day 8	Pre-dose
Cycle 1	* First day of quizartinib administration	2 hours ( $\pm 10$ minutes) post-dose
		4 hours ( $\pm 10$ minutes) post-dose
		6 hours ( $\pm 10$ minutes) post-dose
	Day 9	Pre-dose
	Day 15	Pre-dose
	Day 21	Pre-dose
	* Last day of quizartinib administration	

## 6.9 Anonymization, Storage, and Disposal of Specimens for the Biomarker Study

### 6.9.1 Anonymization of Specimens

The specimens will be anonymized by each of the study centers and the specimen collection agency according to the procedure described below.

The study center will never provide information that can identify individual patients to the specimen collection agency. The anonymity numbers will be strictly stored by the specimen storage manager at the specimen collection agency and will not be provided to the study center.

- 1) The study center will assign a “subject identification code” to each patient. The correspondence table between the “medical record number” and the “subject identification code” that can identify personal information will be stored at the study

center.

- 2) The specimen collection agency will assign an “anonymity number” to the collected specimens of each patient and attach a label displaying the “anonymity number,” in place of the “subject identification code,” to each specimen. The correspondence table between “subject identification code” and “anonymity number” will be prepared by the specimen collection agency and be stored by the sponsor.

#### **6.9.2 Storage and Disposal of Specimens**

The sponsor will be responsible for disposal of the specimens as requested by patients via the investigator and disposal after the end of the storage period. Specimens will be stored for a maximum of up to 3 years after completion of the study.

At the expiration of the storage period, the specimen collection agency and the central laboratory will dispose of the specimens according to the sponsor’s directions. For specimens that the sponsor considers are not necessary to be stored any longer, even during the specimen storage period, the specimen collection agency and the central laboratories will dispose of the specimens according to the sponsor’s directions.

If a patient withdraws consent for the study and requests the study center to dispose of the biomarker specimens during the specimen storage period, the specimens will be disposed of, depending on the location of the specimens at the time of the request, according to the following procedure:

- 1) In cases where the specimens are temporarily stored at the study center:  
The investigator or subinvestigator will identify the specimens of the patient and dispose of them.
- 2) In case the specimens are stored at the specimen collection agency or the central laboratory:  
The investigator or subinvestigator will report the subject identification code of the pertinent patient to the sponsor. The sponsor will identify the specimens of the patient based on the correspondence table linking the subject identification code with the anonymity number, inform the specimen collection agency or the central laboratory of the anonymity number, and direct the agency or laboratory to dispose of the specimens. The specimen collection agency or the central laboratory will dispose of the specimens according to the sponsor’s directions.

Specimens collected for the assessment of FLT3-ITD status and c-KIT mutations of a patient who withdraws consent should be disposed of promptly in accordance with the Ethical Guidelines for Human Genome/Gene Analysis Research. Regarding the other

specimens of the patient, the sponsor will decide on the timing of disposal.

Specimens of a patient who withdraws consent should be managed strictly by separating them from the specimens of other patients until they are disposed of. The sponsor is responsible for the management of the specimens.

## **7. PHARMACOKINETIC ENDPOINTS**

The following pharmacokinetic parameters will be calculated by a non-compartment model approach using plasma concentration data of quizartinib and its active metabolite AC886 obtained on Day 8 of Cycle 1 and Day 21 of Cycle 1 during the induction phase.  
Day 8 of Cycle 1 during the induction phase: Cmax, Tmax, AU $\tau$

Day 21 of Cycle 1 during the induction phase: Cmax,ss, Ctrough, Tmax,ss, AU $\tau$ ,ss

The details of the method of calculation of pharmacokinetic parameters are specified in the Statistical Analysis Plan.

## **8. PHARMACODYNAMIC ENDPOINTS**

The following endpoints will be measured:

- FLT3-ITD status and c-KIT mutations (bone marrow liquid or blood specimens)
- Phosphorylated FLT3, STAT5, and c-KIT protein levels in blood (blood specimens)
- Inhibitory activity of plasma quizartinib on phosphorylated FLT3 protein (plasma specimens)

## **9. SAFETY ENDPOINTS**

Safety endpoints are defined as AEs, laboratory data, body weight, vital signs, and 12-lead ECG.

### **9.1 Definition of Adverse Events**

An AE is any untoward or unintended sign (including an abnormal change in laboratory findings or vital signs), symptom, or disease noted between the day of informed consent for the study and the end day of post-treatment observation, whether it is considered to be related to the study drug or not.

A symptom or disease preexisting before informed consent for the study is obtained will be handled as a complication, not as an AE. Any complication that is exacerbated after informed consent for the study is obtained should be handled as an AE, and the date when the exacerbation is detected will be recorded as the date of onset of the AE.

The progression of the underlying disease (AML) will be handled as described below:

- Tumor progression will not be handled as an AE, in principle. However, tumor progression leading to the outcome of death during the AE collection period should be handled as an SAE (with the name and outcome of the event recorded as “disease progression” and “fatal,” respectively).
- Tumor progression resulting in exacerbated signs or symptoms will be handled as an AE.

### **9.2 Definition of Serious Adverse Events**

An SAE is any AE that:

- results in death,
- is life-threatening,
- requires inpatient hospitalization or prolongation of existing hospitalization for treatment,
- is a disability or incapacity,
- may lead to a disability or incapacity,
- represents other medically important condition, or
- is a congenital anomaly or birth defect.

### **9.3 Adverse Event Information to Be Reported**

If an AE occurs during the study, the items shown in “Table 9.3-1 Investigation Items following Onset of Adverse Events” will be investigated and recorded in the CRF, etc.

Only the highest grade observed in the course of each AE should be recorded as the severity in the CRF.

Table 9.3-1 Investigation Items following Onset of Adverse Events

Item	Details to Be Investigated	
AE	Name of AE, date of onset	
Intervention for AE	Presence or absence of intervention (including changes in study drug administration), and if present, the content of the intervention	
Outcome	Outcome category, date of outcome assessment, date of resolution	
Severity	Recovered/ Resolved	The AE has resolved, and the patient has recovered to the pre-event condition.
	Recovering/ Resolving	The AE has almost resolved, and the patient has nearly recovered to the pre-event condition.
	Not recovered/ Not resolved	The AE has not resolved, and the condition of the patient is similar to that at onset (unchanged).
	Recovered/ Resolved with sequelae/residual effect(s) present	The AE has resolved, but the patient has sequelae.
	Fatal	The event outcome is fatal only when the investigator considers that the AE and the patient's death are related or that a relationship cannot be ruled out. Death due to worsening of the underlying disease is not applicable to this category.
	Unknown	Outcome is unknown because of lack of information.
Seriousness	To be assessed according to the CTCAE v4.0 Japanese version. The severity of AEs not included in the CTCAE v4.0 Japanese version will be assessed according to the following grades:	
	Grade 1	Mild; asymptomatic or mild symptoms; clinical or diagnostic observations only; intervention not indicated.
	Grade 2	Moderate; minimal, local or noninvasive intervention indicated; limiting age-appropriate instrumental ADL.
	Grade 3	Severe or medically significant but not immediately life-threatening; hospitalization or prolongation of hospitalization indicated; disabling; limiting self care ADL.
	Grade 4	Life-threatening consequences; urgent intervention indicated.
	Grade 5	Death related to AE.
Causality with the study drug and coadministered drugs (cytarabine and the anthracycline drug)		
Causality category	Related	
 
There is a reasonable temporal relationship between the onset of the AE and administration of the study drug, it is not reasonable to assess that the AE is attributable to the patient's condition or other factors than the study drug (underlying disease, complications, concomitant drugs, etc.), and a relationship with the study drug cannot be ruled out.
 
There is a reasonable temporal relationship between the onset of the AE and administration of the study drug, and the AE can be explained by known actions or the pharmacological action of the study drug or similar analogues.
 

	Unrelated	
 
There is no reasonable temporal relationship between the onset of the AE and administration of the study drug, it is reasonable to assess that the AE is attributable to the patient's condition or other factors than the study drug (underlying disease, complications, concomitant drugs), and a relationship with the study drug can be ruled out.
 

#### **9.4 Definition of Adverse Drug Reactions**

AEs that are assessed as “related” to the study drug will be handled as adverse drug reactions.

#### **9.5 Actions to Be Taken for Adverse Events**

##### **9.5.1 Recommended Action for Adverse Events**

If any AE has occurred, the investigator or subinvestigator will take appropriate actions, notify the sponsor as required, and continue follow-up until the patient recovers to the pre-event condition with resolution or relief of the AE as far as possible, even after the end of this study. However, even if the AE is not confirmed to have resolved or relieved, if it is judged that the patient’s condition remains stable and the safety can be assured, the investigator or subinvestigator will explain the matter to the patient, and the follow-up of the study will be completed (treatment of the relevant symptom will be continued).

##### **9.5.2 Action for Serious Adverse Events**

If an SAE has occurred, the investigator or subinvestigator will take appropriate actions, and report the details of the SAE to the sponsor by telephone or fax within 24 hours of learning of the occurrence. The investigator will subsequently enter the necessary information in the Serious Adverse Event Report (SAVER) FORM (Appendix 3) and submit the form with the date of confirmation and a signature to the sponsor without delay. A written report to the head of the study center will be made in accordance with the procedures and format specified by the study center.

#### **9.6 Actions to Be Taken in the Event That Information on Pregnancy, Pregnant and Parturient Women, and Delivery Is Obtained**

If information on the pregnancy of a patient or a patient’s female partner is obtained during the study period or within 6 months after the last dose of the study drug, the investigator or subinvestigator will investigate the information on the pregnancy through delivery, and report it to the sponsor using the format provided by the sponsor (Appendix 4). Pregnancy will not be handled as an AE; however, if the outcome of the pregnant woman falls under the definition of SAEs (congenital anomaly in the fetus [including suspected cases], stillbirth, and abortion), the investigator or subinvestigator must report it to the sponsor in accordance with the procedures for reporting SAEs specified in “9.5.2 Action for Serious Adverse Events,” independent of whether it is during the study period or not.

## 10. EFFICACY ENDPOINTS

The antitumor effect of quizartinib will be assessed based on bone marrow findings and neutrophil and platelet counts in the peripheral blood, as specified in “10.1 Definition of Efficacy Endpoints.”

### 10.1 Definition of Efficacy Endpoints

The efficacy endpoints are defined as follows:

Table 10.1-1 Definition of Efficacy Endpoints

Complete remission (CR)	For patients to be classified as CR, they must achieve a morphologic leukemia-free state, must have $< 5\%$ bone marrow blasts in the bone marrow, a neutrophil count $\geq 1000 / \text{mm}^3$ , and a platelet count $\geq 100\,000 / \text{mm}^3$ , must be independent of RBC and platelet transfusions (defined as 4 weeks without RBC transfusion and 1 week without platelet transfusion), and may not have extramedullary leukemia.
CR with incomplete platelet recovery (CRp)	For patients to be classified as CRp, they must fulfill all the criteria for CR, except for incomplete platelet recovery ( $< 100\,000 / \text{mm}^3$ ).
CR with incomplete hematological recovery (CRI)	For patients to be classified as CRI, they must fulfill all the criteria for CR, except for incomplete hematological recovery with residual neutropenia $< 1000 / \text{mm}^3$ . Platelet recovery status and RBC and platelet transfusion independence are not required.
Partial remission (PR)	For patients to be classified as PR, they must have bone marrow regenerating normal hematopoietic cells, no or minimal residual blast cells in the peripheral blood, a decrease of at least 50% in the percentage of blasts in the bone marrow aspirate, and total marrow blasts between 5% and 25% inclusive.
No response (NR)	NR is defined as a condition not reaching any of CR, CRp, CRI, or PR.
Composite CR rate (CRC rate)	Composite CR rate (CRC rate) is defined as the proportion of patients whose best response is any of CR, CRp, and CRI.
Response rate	Response rate is defined as the proportion of patients whose best response is any of CR, CRp, CRI, and PR.
Relapse	
Relapse after CR, CRp, or CRI: Defined as the reappearance of leukemic blasts in the peripheral blood or an increase in the percentage of blasts in the bone marrow aspirate to <math>\geq 5\%</math>, or the reappearance or new appearance of extramedullary leukemia.
 
Relapse after PR: Defined as the reappearance of significant numbers of blasts in the peripheral blood or an increase in the percentage of blasts in the bone marrow aspirate to <math>> 25\%</math>, or the reappearance or new appearance of extramedullary leukemia.

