### 10.2 Best Response

Best response is defined as the best measured response (CR, CRp, CRI, PR, or NR) over all response assessments at all time points after the start of study treatment.

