## **11. STATISTICAL ANALYSES**

An outline of the statistical and pharmacokinetic analyses is provided below. Details will be specified in the Statistical Analysis Plan.

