#### **11.3.3 Efficacy Analysis**

In the Efficacy Analysis Set, frequency tables will be prepared for CR, CRp, CRi, PR, and NR at each time point as well as for best response. The CRc rate (CR + CRp + CRi), response rate (CRc + PR), and their 95% confidence intervals will be calculated.

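### Read as written, Table 10.1-1 classes a transfused patient with a leukemia-free marrow as NR if neutrophils have recovered, but as CRi if they have not

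*Combined protocol and SAP*

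**What the plan says.** Table 10.1-1 in Section 10.1 sets the response classes.

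- **CR** needs a leukemia-free marrow with under 5% blasts, neutrophils of at least 1000/mm³, platelets of at least 100 000/mm³, no extramedullary leukemia, and independence from RBC and platelet transfusion, "defined as 4 weeks without RBC transfusion and 1 week without platelet transfusion".
- **CRp** keeps every CR criterion except the platelet count, so transfusion independence still applies.
- **CRi**: "they must fulfill all the criteria for CR, except for incomplete hematological recovery with residual neutropenia" below 1000/mm³. A second sentence adds: "Platelet recovery status and RBC and platelet transfusion independence are not required".
- **PR** needs 5% to 25% marrow blasts.
- **NR** is the remainder: "NR is defined as a condition not reaching any of CR, CRp, CRI, or PR".

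Section 10.2 takes the best class "over all response assessments at all time points after the start of study treatment". Under Section 11.3.3, "frequency tables will be prepared for CR, CRp, CRi, PR, and NR at each time point as well as for best response", and the CRc rate and response rate are reported with 95% confidence intervals. Section 11 adds: "Details will be specified in the Statistical Analysis Plan". The supplied text contains no fuller definition of CRi.

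**The concern.** The only waiver of transfusion independence sits in the row that is tied to residual neutropenia. A patient whose marrow is clear and whose neutrophils have recovered, but who was transfused recently, fails CR and CRp on transfusion, CRi on neutrophils and PR on blasts. What remains is NR. If that patient's neutrophils had stayed below 1000/mm³, the class would be CRi. The scale then runs the wrong way in neutrophils, and two analysts who read the CRi row differently would tabulate the same patient as a remission and as a non-response.

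At stake are the class tables at each visit and, less often, the CRc and response rates.

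**Working it through.** The plan gives no figure to reproduce. The check is to apply the table as a rule and then size the effect.

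**Step 1. Enumerate.** Fix a leukemia-free marrow, blasts under 5% and no extramedullary leukemia. PR is then impossible, since it needs at least 5% blasts. Three yes/no items remain, giving 2 × 2 × 2 = 8 combinations. Independent means no RBC transfusion for 4 weeks and no platelet transfusion for 1 week.

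| Neutrophils ≥1000 | Platelets ≥100 000 | Transfusion independent | Neutropenia required | Neutropenia permitted, classes in order CR, CRp, CRi |
|---|---|---|---|---|
| yes | yes | yes | CR | CR |
| yes | yes | no | **NR** | CRi |
| yes | no | yes | CRp | CRp |
| yes | no | no | **NR** | CRi |
| no | yes | yes | CRi | CRi |
| no | yes | no | CRi | CRi |
| no | no | yes | CRi | CRi |
| no | no | no | CRi | CRi |

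Neutropenia required: CR 1, CRp 1, CRi 4, NR 2. Neutropenia permitted, in order: CR 1, CRp 1, CRi 6, NR 0. Six cells agree; the two NR cells change. Without an order, the permissive reading leaves two cells (the CR cell and the CRp cell) that also meet the CRi text. The cells are not equally likely, so 2 of 8 is not a frequency.

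**Step 2. Where the condition can arise.** The first marrow assessment on treatment is Day 21 of induction Cycle 1 (Section 6.2). Looking back 28 days gives 21 − 28 = −7, about a week before Day 1. Any RBC transfusion in the cycle up to that visit therefore breaks independence. Such a patient, if neutrophils have recovered, would go on to consolidation under the myeloblast rule in Section 6.2 and yet be tabulated as NR at that visit.

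**Step 3. Effect on the rates.** A per-visit NR is superseded if the patient reaches a better class at another assessment (Section 10.2).

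- CR, CRp or CRi at another assessment: neither rate changes.
- PR as the best class elsewhere: the response rate is unchanged, and CRc alone moves by 1/n.
- None of the four at any other assessment: both rates move by 1/n.

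With the 6 to 12 patients of Section 11.5, and assuming that all enter the Efficacy Analysis Set, 1/12 = 8.3 points and 1/6 = 16.7 points.

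**Step 4. Illustration.** Assumed counts, one affected patient, exact (Clopper-Pearson) 95% intervals:

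| n | Literal reading | Neutropenia permitted |
|---|---|---|
| 12 | 9/12 = 75% (43 to 95%) | 10/12 = 83% (52 to 98%) |
| 6 | 4/6 = 67% (22 to 96%) | 5/6 = 83% (36 to 99.6%) |

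The intervals overlap heavily.

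**The case against.** The strongest reply is that the second CRi sentence can be read as a general waiver, with neutropenia as one allowed deficit. On that reading the anomaly disappears, and the Statistical Analysis Plan may say so. This stands in part: the reading is possible. But it is not stated in the supplied text, and the CRi clause is built like the CRp clause, where the low count defines the class.

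The second reply is that the consequence is remote. This largely stands. Marrow is assessed in every cycle and at withdrawal, and best response absorbs an isolated NR. Section 1.3.2 reports delayed recovery of neutrophils as well as platelets, which points to the CRi cells more often than the NR cells.

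The third reply is that class order is a small matter, since CRc sums all three classes. That is correct for CRc and the response rate; order matters only for the separate CR, CRp and CRi counts.

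A reader might also infer that the plan overlooks transfusion status, because Section 10 says the antitumor effect "will be assessed based on bone marrow findings and neutrophil and platelet counts in the peripheral blood". The documents do not support that. Sections 10, 6.2 and 6.3 all refer to Section 10.1, which contains the transfusion criteria, and Section 6.1 provides for recording transfusions after consent.

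**Conclusion.** The point holds as a defect of wording, at low to moderate priority and for the exploratory efficacy analyses only. Followed as written, the table gives a worse class for better neutrophil recovery in two of the eight combinations. The tables by time point are affected at each such visit. The two summary rates both move, by 8.3 to 16.7 points per patient, only for a patient with none of CR, CRp, CRi or PR at any other assessment. This rests on the plain reading of the CRi row and on the planned 6 to 12 patients; how often the case arises is unknown and probably low.

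Two stronger conclusions are tempting and are not supported. One is that the reported CRc and response rates will be materially too low: nothing in the documents shows that such a patient is likely, and every count in the illustration is assumed. The other is that the dose decision is compromised: the DLT and MTD rules in Section 5.4 do not use these classes, and entry to consolidation depends on the myeloblast percentage (Section 6.2).

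**What to change.** For the efficacy analyses (Sections 10.1, 10.2 and 11.3.3), assign classes in the order CR, CRp, CRi. State that a patient with a leukemia-free marrow, under 5% blasts and no extramedullary leukemia who misses CR and CRp only on neutrophil count, platelet count or transfusion independence counts as CRi. This leaves none of the eight combinations NR and none in two classes. It costs one or two sentences and no new data for CRc. If the Statistical Analysis Plan already settles the point, a cross-reference is enough.

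The downside should be disclosed: the change can only raise CRc and the response rate or leave them unchanged, and it may depart from what the sponsor intended. If the literal rule is intended, confirm it in the table.

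Sections 5.6 and 6.3 also use CR, CRp and CRi, in connection with stopping study treatment for HSCT. Those passages must be reconciled with the clarified table; no clinical rule is proposed here.

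A separate and lesser addition: keep the Section 11.1.2 set, and add one row giving CRc and response rate among everyone who took study drug, counting those without a post-treatment assessment as non-responders. With one such patient and assumed counts, 9/11 = 82% becomes 9/12 = 75%, and 4/5 = 80% becomes 4/6 = 67%. The downside is a slightly less favourable rate. Few patients should be affected, because Section 6.4 already calls for an assessment at withdrawal.
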